Data for this study will be recorded on a secure password-protected electronic database called **Exemplo**. Data entry will be done by study investigators and/or data analysts who are part of the approved IRB team. Unidentified data may be shared with the sponsor, Boehringer Laboratories LLC.

Data analysis will be done by internal or externally hired statisticians on de-identified data on spreadsheets downloaded from **Exemplo**.

Separate intra-operative data will be collected from the EHR either via the Operative Note or via standardized PowerNote templates (**if available**) to help capture data pertinent during sleeve gastrectomy including the following:

- 1) Patient Full Name: pre-populated/pull from eEMR
- MRN: pre-populated/pull from eEMR
- 3) **Date of surgery**: pre-populated/pull from eEMR
- 4) **Primary Surgeon**: pre-populated/pull from eEMR
- 5) **Stapler used**: Echelon Flex Powered 60mm stapler, Endo GIA 60 mm Universal Stapler XL; Other (free text)
- 6) **Distance from pylorus for 1**st **stapler firing**: Free text for centimeters
- 7) **Calibration device**: EGD/Standard Weighted Bougie Tapered/Standard Weighted Bougie Blunt/ViSiGi device/Other (free text)
- 8) Calibration device size: free text for French
- 9) Total number of stapler load firings: free text number
- 10) **Length of stapler loads used** (list number): 60 mm(free text number or click n/a); 45 mm (free text number or click n/a); other (free text)
- 11) **Number, order & color of stapler loads** (first to last; i.e. 2 green, 2 gold, 1 blue): free text
- 12) Use of Seam Guard reinforcement for stapler loads: yes/no
 - a. If yes, were all stapler loads reinforced? Yes/no; other (free text)
- 13) Other procedures performed:

- a. Plication/imbricating suture to sleeve: yes/no; other (free text)
- b. Pexy of omentum to sleeve: yes/no; other (free text)
- c. Clipping of sleeve staple line: yes/no; other (free text)
- d. Oversewing staple line: yes/no; other (free text)
- e. Fibrin glue to staple line: yes/no; other (free text)
- f. Any other procedures?: free text

14) **EGD done**: yes/no

- a. If yes, any abnormal findings: yes/no; other (free text)
- b. If abnormal findings, please list any interventions done: free text
- 15) Miscellaneous Notes: free text

13. Statistical Analysis

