There will be 50 patients undergoing LSG with an endoscope and 50 patients undergoing LSG with a suction calibration system. Both methods are clinically accepted and approved methods of performing the procedure. The target enrollment will be 125 to account for attrition due to screen failures, early withdrawals, etc. For this study we use a randomized block design (RBD) to assign participants to one of two sleeve groups. In a RBD we divide participants into subgroups called blocks (e.g. gender, race, etc.), such that the variability within blocks is less than the variability between blocks. Then, subjects within each block are randomly assigned to treatment conditions (i.e. SG with EGD or SG with ViSiGi device). The purpose of the RBD is to help reduce variability within treatment conditions and potential confounding from blocking factors, producing a better estimate of treatment effects. We are adequately powered to detect a mean difference in stapler load firings of 0.4 between groups assuming a standard deviation of 0.7, which is consistent with our institutional sleeve gastrectomy experience. After all cases have been performed statistical methods will be implemented to determine any difference in outcomes. An initial approach will focus on a pairwise analysis (t-test) between the ViSiGi and EGD calibration groups for each of the primary and secondary aims. A more comprehensive multivariate analysis factoring in demographic and clinical variables will be performed to further delineate significant differences in the 2 sleeve gastrectomy methods. In the unlikely situation that an adverse event occurs, the event will be inspected to determine if an early stoppage is necessary.

14. Provisions to Monitor the Data to Ensure the Safety of Participants

All methods used in this study for performing sleeve gastrectomy are already approved and clinically accepted. Validated users of the device will be attending surgeons who have been trained using the ViSiGi device via online video-based education

(https://www.youtube.com/watch?v=zDhc-1fr32E), review of the manufacturer instructions for use (IFU) sheet below:

(chromeextension://oemmndcbldboiebfnladdacbdfmadadm/https://www.boehringerlabs.com/wp-content/uploads/2018/09/5232009.pdf) as well as in-person education via representatives from Boehringer Laboratories, LLC.

All surgeons will be required to complete the video-based module and review the IFU sheet prior to using the ViSiGi device.

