The PI will be responsible for ensuring participants' safety on a weekly basis as cases are performed (sleeve gastrectomies are not always done every week) and for reporting serious Adverse Events (AEs) and Unanticipated Problems (UPs) to his or her Institutional Review Board (IRB) and the monitoring body with the help of the study coordinator. The study coordinator and/or PI will prepare reports that list AEs, serious AEs, deaths, and disease-or treatment-specific events required for MB review in order to ensure good clinical care and identify any concerning trends. The Monitoring Body (MB) will act in an advisory capacity to the PI to monitor participant safety, evaluate adverse events and progress of the study. The MB will constitute two surgeons who are not directly involved in the study protocol but participate in the care of bariatric patients at Emory University Hospital Midtown and will to review the safety data annually.

The PI will be informed of serious AEs as soon as they occur by Co-Investigators (i.e., surgeons performing sleeve gastrectomy) and/or the study coordinator and notify the MB within 48 hours of becoming aware of the event. The PI will report serious AEs and UPs to his or her IRB within 5 business days of becoming aware of the event. Events constituting UPs include calibration device malfunctions such as a piece or component of the device breaking off into the stomach during manipulation, failure of the device to adequately perform a leak test, or contamination or damage to the device such that it cannot be appropriately used. Specific triggers for an ad hoc review or initiation of the process of an ad hoc review will occur if there are unforeseen deaths or if there is a serious AE including stapling across a calibration device during sleeve gastrectomy or other serious device malfunction leading to patient injury. At any point during the study time period, the study will be stopped and undergo further review if ≥ 1 deaths or a serious AE directly related to calibration device use (i.e., stapling across device while creating sleeve gastrectomy or serious device malfunction leading to patient injury) occurs.

Safety reports will be sent to the MB for review after the first 5 subjects are enrolled and within 12 months of the study start date. Safety assessment reports will provide a

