detailed analysis of safety issues including the incidence of AEs, clinical severity of AEs, serious AEs, UPs, deaths and protocol deviations. The PI will also document receipt and review of these safety reports in addition to any corrective actions and/or resolutions to findings reported which will also be reported to the IRB.

The sponsor does not have any additional reporting requirement than what Emory Hospital already has in place.

15. Economic Burden to Participants

N/A

16. Informed Consent Process

Consent will be obtained in person before the patient undergoes surgery by the principal investigator, co-investigators, and/or research study coordinator. Consent will likely occur at the initial surgical consultation, but may be obtained at any point prior to randomization. Patients will be notified if they are going to be in the EGD vs. ViSiGi device arm of the sleeve gastrectomy protocol during the perioperative period; it will be explained to them that this selection is being done in a randomized fashion, similar to flipping a coin, factoring in various patient-related factors. No elements of HIPAA will be waived. The study participants are legal adults and not pregnant, prisoners, or otherwise cognitively impaired in any way.

DocuSign:

The study team will use an Emory DocuSign account that is HIPAA compliant and meets the FDA's requirement for CFR Part 11 signatures. The consent process begins when a patient is screened and identified as eligible for study participation. A member from the study team will discuss the informed consent form in its entirety with the potential participant via telephone phone and/or Zoom. The patient's identity will be verified by requesting that he/she confirm their demographical information (i.e. full name, DOB, address, etc.).

In DocuSign, potential subjects have the ability to review the consent document as freely as they would if they were consenting in person. They also have the opportunity to exit the document without signing. The patient will be offered ample time to discuss the informed consent form with family and or friends, and have questions answered.

The process for obtaining final consent is outlined below:

1. First, the IRB-approved, stamped informed consent form(s) are added to an envelope in DocuSign.

- Secondly, recipients (subjects/coordinators) are then added to the envelope and signature and initial fields are assigned to them on the IRB approved informed consent form.

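### The trial randomises in blocks to reduce variability, but the primary t-test carries no block term, and surgeon is named neither as a blocking factor nor as a covariate

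*Combined protocol and SAP*

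**What the plan says.** **Design.** Section 13 states: "For this study we use a randomized block design (RBD) to assign participants to one of two sleeve groups". Blocks are described as "subgroups called blocks (e.g. gender, race, etc", and "subjects within each block are randomly assigned to treatment conditions". The stated aim is: "The purpose of the RBD is to help reduce variability within treatment conditions and potential confounding from blocking factors". There is no final list of factors or levels, no block size and no sequence method. Section 16 says patients will be told that assignment is "similar to flipping a coin, factoring in various patient-related factors".

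**Analysis.** Section 13 begins with a t-test between the two calibration groups for the primary and each secondary aim. A multivariable analysis follows, with demographic and clinical variables that are not listed. Neither step names the blocking factors or surgeon.

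**Surgeons.** Section 14 speaks of "Co-Investigators (i.e., surgeons performing sleeve gastrectomy" and says "All surgeons will be required to complete the video-based module", so more than one surgeon operates; the number is not given. The intra-operative data list in Section 12 includes "Primary Surgeon". The table in Section 4 has an entry on standardising surgeon technique, without detail.

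**Size.** Sections 7 and 13 plan 50 patients per arm. Section 13 bases this on a difference of 0.4 firings and an SD of 0.7.

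**The concern.** A blocked randomisation and an analysis without block terms do not fit together. Blocking improves a comparison when assignment is balanced within blocks, the blocks predict the outcome, and the analysis removes the between-block variation. Section 13 leaves the first two open and omits the third from its leading analysis.

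Surgeon is an obvious candidate that goes unnamed. The operative form in Section 12 leaves open the stapler model, the load length, the distance from the pylorus of the first firing, reinforcement and oversewing. The first three bear on the number of firings; the last two bear on time and cost. If surgeons differ on these, the difference between surgeons sits in the error term of the primary test.

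What is at stake is precision, and some protection against chance imbalance between surgeons, in a trial whose power is only just above 80%. The validity of the test is not at stake.

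**Working it through.** **1. The plan's own size.** Inputs from Section 13: difference 0.4, SD 0.7, 50 per arm. Alpha and power are not stated; I assume two-sided 0.05 and 80%.

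- Normal approximation: n = 2(1.960 + 0.842)² × 0.7²/0.4² = 48.1, so 49 per arm. Power at 50 per arm is 81.5%.
- Noncentral t: 79.96% at 49 per arm and 80.8% at 50.

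The planned size reproduces with the full SD of 0.7. It takes no credit for blocking.

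**2. What a block term can bring.** If balanced factors explain a share R² of the variance and are in the model, the residual SD is 0.7√(1 − R²).

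- Weak factors (normal approximation): R² of 1%, 2% and 5% gives power of 81.9%, 82.3% and 83.4%, against 81.5%.
- Stronger factors (noncentral t): R² of 10%, 20% and 30% gives residual SDs of 0.664, 0.626 and 0.586, and power of 84.7%, 88.6% and 92.2%, against 80.8%.

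**3. Separating randomisation from model.** The documents give neither the number of surgeons nor their variance share. Assumed: 4 surgeons explaining 10%, 20% or 30%. A simulation of 100 patients (6,000 runs per power figure) gave:

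| Assignment | Analysis | 10% | 20% | 30% |
|---|---|---|---|---|
| Unrestricted | t-test | 0.818 | 0.831 | 0.835 |
| Unrestricted | surgeon in model | 0.830 | 0.872 | 0.909 |
| Permuted blocks by surgeon | t-test | 0.831 | 0.845 | 0.864 |
| Permuted blocks by surgeon | surgeon in model | 0.852 | 0.883 | 0.924 |

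The first row drifts above 80.8% because four surgeon effects were drawn afresh in each run. The average variance among the patients is then 0.49(1 − ρ/4), where ρ is the surgeon share; at ρ = 0.3 this is 0.453, an SD of 0.673. With the overall SD held at 0.7, the reference is 80.8%. The gain from the model term alone is then about 2, 6 and 10 points. Against the simulation's own first row it is about 1, 4 and 7 points.

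Adding surgeon-stratified permuted blocks to the model term gives a further 0.852 − 0.830 = 0.022, 0.883 − 0.872 = 0.011 and 0.924 − 0.909 = 0.015.

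**4. Type I error.**

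- Unrestricted assignment with the t-test: 0.049, 0.057 and 0.050 (4,000 runs; simulation error about √(0.05 × 0.95/4000) = 0.003). There is no pattern of inflation.
- Balanced assignment with the t-test: the test uses the full SD although the estimate varies only with the residual SD. With exact balance, the error rate is 2[1 − Φ(1.984/√(1 − ρ))]. This is 0.037, 0.027 and 0.018 for ρ of 10%, 20% and 30%. The simulation, with its varying surgeon effects, gave 0.041, 0.035 and 0.032. The test is conservative.

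**5. Arm sizes under unrestricted assignment.** With a Binomial(100, 0.5) split, exactly 50:50 occurs 8% of the time and a split outside 40–60 occurs 3.5% of the time. Power is 80.4% at 45:55 and 79.2% at 40:60, against 80.8% at 50:50.

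**The case against.** The strongest case against is that Section 13 is brief rather than wrong. The blocking examples form an open list inside a general definition, so surgeon is unnamed but not excluded. A randomised block design ordinarily means balanced assignment within blocks, and the fixed 50 and 50 point the same way. Technique is to be standardised, the sample size does not rely on blocking, and the later multivariable analysis could include surgeon.

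Much of this stands, and it rules out several stronger readings:

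- *The blocking balances nothing.* A reader might infer this from the coin-flip wording and the absence of a block size. That wording describes what patients are told, and silence on the method does not establish unrestricted assignment.
- *Surgeon is the main source of variability.* No figure in the documents supports this. Recording stapler and technique items does not show that surgeons differ on them.
- *Unequal arms threaten the trial.* A 45:55 split costs about 0.4 points of power.
- *The blocking fails to deliver a promised gain.* Section 13 says only that it should help, and puts no number on it.

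What the objection does not answer is the leading analysis. Whatever the blocks turn out to be, the t-test does not contain them. The patient-related factors mentioned in Section 16 also point away from surgeon, and a possible place in an unspecified later model is not a commitment.

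**Conclusion.** The point holds as a mismatch between design and primary analysis, together with an unnamed surgeon factor. If assignment is balanced within blocks that predict firings, the t-test overstates the standard error and is conservative. If assignment is unrestricted, blocking alone yields no gain. In both cases the precision benefit does not fully reach the primary comparison, and type I error is not inflated.

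The size depends on assumptions: two-sided 0.05, an overall SD of 0.7, and 4 surgeons explaining 10% to 30% of the variance. On these, power rises from about 81% to about 83%, 87% or 91% with surgeon in the model, and to about 84–85%, 88–89% or 92% with surgeon stratification as well. Most of the gain comes from the model term. If standardisation works and surgeons hardly differ, the gain is close to nil, but so is the cost. This is an improvement worth making; the trial remains valid without it.

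**What to change.** In Section 13:

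1. Replace the t-test as primary analysis of firings, and of operative time and cost, with a linear model containing treatment, the blocking factors actually used and Primary Surgeon. Keep the t-test as a supporting analysis. Fix this before outcome data are compared by arm.
2. List the blocking factors and their levels, and state how assignment within blocks was or will be generated.
3. For patients still to be randomised, preferably stratify by surgeon with randomly permuted blocks of varying size. If randomisation is complete, make the model change alone.

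Cost: a few degrees of freedom (three for 4 surgeons) and a short rewrite of Section 13, plus a new list for remaining patients if step 3 is taken. Primary Surgeon is already collected, so no new data are needed.

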- Risks/discomforts of EGD and ViSiGi device are comparable. Using a ViSiGi device is similar to both a standard weighted bougie and an EGD calibration technique. The ViSiGi device is similar to a gastroscope in that they both have suction, calibration, and leak testing capabilities. The benefit of the ViSiGi device is that it obviates the need for doing an EGD during sleeve gastrectomy, is single patient use and thus does not require reprocessing, and doesn't require a scope tower to operate it. Potential benefits of using the ViSiGi device (in lieu of endoscopic calibration) in order of highest probability are as follows: 1) less staple loads, 2) shorter OR time, 3) reduced cost, 4) decreased post-op GERD rates.
- Data analyst and study coordinator to have research roles at this time
- Immediate post-op follow-up 3 weeks after surgery (+/- 2 weeks) to 12 months out (+/- 12 months)
 - Assessments made by surgeon will be for diagnostic, therapeutic and research purposes as appropriate
 - Study coordinator and data analyst will function in research roles only
 - Goal in this period is predominantly research purposes only
 - Due to constraints from COVID-19 and decreased in-person follow-up, the 12-month assessment time frame will be extended to 24 months post-surgery to help gather GERD-HRQL and weight loss data
 - a. What type of information will be collected:
 - i. See above table
 - ii. Demographic and clinical variables will be collected at (baseline) including age, gender, race, BMI, smoking status, functional status, and medical comorbidities:
 - 1. EHR
 - 2. MBSAQIP
 - 3. Baseline GERD-HRQL scores (standardized questionnaire)
 - iii. Intra-operative/procedure data (i.e. type of stapler used, # staple load firings, length and color stapler loads, etc.)
 - 1. EHR
 - 2. Research data sheets
 - iv. Post-operative data & assessment
 - 1. EHR
 - 2. MBSAQIP (30-day outcomes and weight loss outcomes)
 - 3. Cost data (administrative data) from internal databases
 - 4. GERD-HRQL scores (standardized questionnaire)

6. Inclusion and Exclusion Criteria

Patients selected for this study will be adults, 18 years old or older, who have already agreed with their surgeon that LSG is the best choice for them. Patients will be excluded by the following criteria;

- Subjects with prior gastric surgery or bariatric surgery (including prior adjustable gastric band and/or sleeve gastrectomy).
- Concomitant hiatal surgery
- Paraesophageal hernia at time of surgery

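### Section 13 randomises within blocks, but its initial test of every aim has no block term, and no analysis tied to the blocks is named as the deciding one

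*Combined protocol and SAP*

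**What the plan says.** Section 13 (Statistical Analysis) describes the allocation: "we divide participants into subgroups called blocks (e.g. gender, race, etc" and so on, with random assignment inside each block. The list of factors is open, and no block size or within-block ratio is given. The stated aim is precision: "The purpose of the RBD is to help reduce variability within treatment conditions and potential confounding from blocking factors", with the result of "producing a better estimate of treatment effects". Section 16 (Informed Consent Process) adds only that the random selection takes various patient factors into account.

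For the analysis, Section 13 says: "An initial approach will focus on a pairwise analysis (t-test) between the ViSiGi and EGD calibration groups", and applies this "for each of the primary and secondary aims". It continues: "A more comprehensive multivariate analysis factoring in demographic and clinical variables will be performed". No covariates are listed for that analysis, the blocking factors are not mentioned in it, and neither analysis is labelled primary. The table in Section 4 gives the statistician's input as still to be determined. Section 5 lists the baseline variables to be collected: "age, gender, race, BMI, smoking status, functional status, and medical comorbidities", and also "Baseline GERD-HRQL scores (standardized questionnaire").

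**The concern.** A blocked design gains precision in two steps. Balancing the arms within blocks makes the treatment difference itself less variable. Removing between-block variation from the residual then lets the standard error show it. A two-sample t-test takes the first step but not the second: its pooled variance still contains the block-to-block differences. When those differences are real, the reported interval is wider than it needs to be and the p-value is too large.

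The multivariate analysis could repair this, since gender and race are both collected, but nothing requires it to include the factors actually used for blocking. The plan also does not say which result stands if the t-test and the model disagree.

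**Working it through.** **Inputs.** From Section 13: 50 per arm, difference 0.4 firings, SD 0.7, enrolment 125. Assumed, because not stated: two-sided 5% level, 0.7 as the total SD, normal errors, and R², the share of outcome variance that the blocks explain.

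**The plan's own figure.** n per arm = 2 × (1.960 + 0.842)² × 0.7² / 0.4² = 48.1, so 49; the exact t calculation gives 49.05, so 50. Power at 50 per arm is 80.8% (noncentral t) or 81.5% (normal approximation). Enrolment: 100 / 0.80 = 125. The planned size reproduces.

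**t-test precision.** SE = 0.7 × √(2/50) = 0.140. The 95% half-width is 1.984 × 0.140 = 0.278 firings.

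**Arms balanced within blocks.** The true SE of the difference is 0.140 × √(1 − R²), but the t-test still works with about 0.140. Its true type I error is therefore about 2 × [1 − Φ(1.960 / √(1 − R²))]. At R² = 10%: 1.960 / 0.949 = 2.066, giving 3.9%.

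t-test power uses the true SE in the numerator. Its pooled variance follows a noncentral chi-square on 98 df with noncentrality 100 × R² / (1 − R²). Block-adjusted power is noncentral t with residual SD 0.7 × √(1 − R²) and 97 df (a two-level factor).

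| Assumed R² | t-test type I error | t-test power | Adjusted power | Gain (points) | Adjusted half-width |
|---|---|---|---|---|---|
| 0% | 5.0% | 80.8% | 80.8% | 0 | 0.278 |
| 5% | 4.4% | 81.3% | 82.7% | 1.4 | 0.271 |
| 10% | 3.9% | 81.9% | 84.7% | 2.8 | 0.264 |
| 20% | 2.8% | 83.3% | 88.5% | 5.2 | 0.249 |

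Four balanced cells give the same gains to within about 0.1 point and cost under 0.1 point at R² = 0. In simulation the adjusted test stayed at about 5%, and the mean estimate was 0.400 under both analyses.

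**Arms not balanced within blocks.** In simulation the t-test keeps about 5% type I error. Adjusted minus t-test power, in points:

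| Levels | R² 0% | R² 5% | R² 10% | R² 20% |
|---|---|---|---|---|
| 2 | −0.4 | 1.5 | 3.5 | 7.6 |
| 4 | −1.2 | 0.7 | 2.8 | 6.9 |

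Break-even is near R² = (levels − 1) / 99, that is about 1% for two levels and 3% for four.

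**What these R² values require.** For two equal-sized levels that differ by d firings, the between-level variance is d²/4, so R² = (d / 1.4)². R² of 5%, 10% and 20% needs d of about 0.31, 0.44 and 0.63.

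**The case against.** The strongest reply is that nothing promised is lost. The t-test is unbiased and does not inflate type I error. With 0.7 as the total SD, its power rises with R² under balance, from 80.8% to 83.3% in the table. With an equal ratio in every block, the simple difference in means is the block-adjusted estimate, so blocking does improve the estimate; only the reported standard error misses the gain. All of this stands.

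The conservatism also needs balance within blocks. A block design normally implies it, but Section 13 says only that assignment within blocks is random. This stands too, and it limits the claim about type I error. It does not remove the case for adjustment, which gains power without balance once R² passes the small break-even value.

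The larger gains need strong predictors: at R² of 10% or more, a two-level factor must shift firings by more than the 0.4 treatment effect. The documents support no particular value. Several factors together, or secondary outcomes, could explain more, but that is not quantified here.

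Finally, the t-test is only the initial approach, and the example blocking factors are demographic variables that the later model may include. That narrows the gap without closing it: inclusion is not required, and the deciding analysis is not named.

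**Conclusion.** The point holds as a modest, nearly free improvement. The plan randomises by blocks, does not commit to analysing by them, and does not say which analysis answers the primary aim. Under balance, the price is a conservative test and 1.4 to 5.2 points of power forgone for R² of 5% to 20%, and nothing at R² = 0. Without balance, type I error stays near 5% and the gain from adjustment is of similar size.

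Three stronger readings are not supported:

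- A reader might infer that the t-test is invalid or biased. It is neither; any error in level is towards caution.
- A reader might infer that the trial is underpowered, or that 81% leaves too little margin. The t-test keeps about 81% or more at every R² examined under balance, and about 80% or more without it.
- A reader might infer that surgeon must also be in the model. Surgeon is a planned data field (Section 12, item 4), but the open blocking list does not show whether it is blocked. An unblocked surgeon term that explains nothing loses power, so it is not part of this point.

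The figures rest on the assumed two-sided 5% level, the assumed R² values, and reading 0.7 as a total SD. If 0.7 were the within-block SD, balanced t-test power at R² = 10% would be about Φ(0.4/0.140 − 2.066) = Φ(0.791) = 78.5%, against 81.5% adjusted (both normal approximation).

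**What to change.** In Section 13, before outcomes are analysed:

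- List the blocking factors actually used, and state the within-block ratio.
- Add wording such as: *The primary analysis is a linear model of the number of firings on arm and the blocking factors (main effects). The arm coefficient and its 95% confidence interval answer the primary aim. The two-sample t-test is a sensitivity analysis.*
- Use the same block terms for operative duration and cost. For the GERD outcome add the baseline GERD-HRQL score, and for the weight outcomes add baseline BMI.
- Label the wider multivariate analysis secondary.

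This costs a few sentences and a few degrees of freedom. If arms are balanced within blocks, the loss is under 0.1 point of power even when the factors explain nothing. If they are not balanced, for example after attrition, the worst case at R² = 0 is roughly 0.4 point for two levels and 1.2 points for four. Section 5 already collects gender, race, BMI and baseline GERD-HRQL. Whether every actual blocking factor is collected cannot be confirmed until the factors are listed.
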